#### 7.1.2. Effectiveness Endpoints

- Cumulative percent of patients who become pregnant over the 6 month observation period and rate of pregnancies per 100 person-years of follow-up.
- The patient response to endometriosis pain treatment: endometriosis pain treatment effect will be measured by visual analogue scale scores recorded by the subjects at each visit. The subject will be asked to indicate the subjective level of endometriosis pain looking back at the last 3 months and mark it with a single vertical mark on the 100mm horizontal visual analogue scale, where 0 mm represents absence of pain and 100mm indicates unbearable pain.

### 7.2. Setting

Subjects will be enrolled by continuous registration method. The investigators will assess all the subjects in their practice who receive at least 1 dose of Sayana® 104mg/0.65mL agreed to participate in this study by signing the 'data privacy statement'. All subjects enrolled should meet the usual prescribing criteria for as Sayana® per the local product document and should be entered into the study at the investigator's discretion.

A written, Pfizer and institutional review board (IRB)/independent ethics committee (IEC)-approved, informed consent (ie, Data privacy statement) must be obtained before initiating study procedures.

The eligibility of the subject will be evaluated. After inclusion of the subject and after obtaining written informed consent (ie, Data privacy statement) (prior to any procedure being performed) from the subject or subject's parents/ legal representative (as appropriate), the investigator or site staff will record the subject data into source documents and into a Case Report Form (CRF). Enrollment visit is the visit when subject signs on informed consent (ie, Data privacy statement). Following the baseline data collection , the visits are at the discretion of the investigator and may follow the local usual standard of care, however, the sponsor recommends safety and treatment data

assessments at 3 month intervals (every 12~14weeks) at a minimum during the 6 months of participation. A Follow-up Call is to be conducted by investigator or delegated staffs at least 28 calendar days after the last administration of the study drug within the observational period in order to collect information on the occurrence of adverse events and concomitant medications.

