## 7. RESEARCH METHODS

### 7.1. Study design

This study is an open-label, non-comparative, observational, non-interventional, prospective and multi-center study in which subjects administered Sayana® (administered as part of routine practice in Korean health care centers by accredited physicians) will be observed prospectively for a period of 6 months from the enrollment date. The visit schedule or interval will be decided by the investigator.

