### **7.5. Study size**

More than 600 subjects should be observed per “Basic Standards for the Re-examination of New Medicines” (Korea MFDS notification No. 2016-97, 2016.9.6., Amendment)

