##### Exposure during pregnancy

An exposure during pregnancy (EDP) occurs if:

1. A female becomes, or is found to be, pregnant either while receiving or having been exposed to (e.g., environmental) Sayana®, or the female becomes, or is found to be, pregnant after discontinuing and/or being exposed to Sayana® (maternal exposure).

An example of environmental exposure would be a case involving direct contact with a Pfizer product in a pregnant woman (e.g., a nurse reports that she is pregnant and has been exposed to chemotherapeutic products).

2. A male has been exposed, either due to treatment or environmental exposure to Sayana® prior to or around the time of conception and/or is exposed during the partner pregnancy (paternal exposure).

As a general rule, prospective and retrospective exposure during pregnancy reports from any source are reportable irrespective of the presence of an associated AE and the procedures for SAE reporting should be followed.

If a study participant or study participant's partner becomes, or is found to be, pregnant during the study participant's treatment with Sayana®, this information must be submitted to Pfizer, irrespective of whether an adverse event has occurred using the NIS AEM Report Form and the EDP Supplemental Form.

In addition, the information regarding environmental exposure to Sayana® in a pregnant woman (e.g., a subject reports that she is pregnant and has been exposed to a cytotoxic product by inhalation or spillage) must be submitted using the NIS AEM Report Form and the EDP supplemental form. This must be done irrespective of whether an AE has occurred.

Information submitted should include the anticipated date of delivery (see below for information related to termination of pregnancy).

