5.2 EFFICACY ANALYSIS SET

Subject who have been administered Sayana® at least once and evaluated upon its related efficacy endpoints at least once will be included in the efficacy analysis set. The efficacy analysis set is a subset of the safety analysis set.

The following cases are excluded from the efficacy analysis set:

- Subjects excluded from safety analysis set listed in section 5.1
- If the purpose of administration was the prevention of pregnancy in women of child bearing potential, subjects whose check either pregnant or not pregnant at evaluation date on the CRF are not completed
- If the purpose of administration was management of endometriosis-associated pain, subjects whose record VAS score at baseline or evaluation date on the CRF are not completed

Unless specified otherwise, statistical analysis on efficacy parameters will be performed on the efficacy analysis set.

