8.2.2 Efficacy Analysis

The cumulative percent of patients who become pregnant by month 6 will be calculated as $100*(1 - \text{Kaplan-Meier curve at month 6})$, where the Kaplan-Meier (KM) method for estimating survival function will be applied to time-to-pregnancy. Patients who did not become pregnant will be censored at the time of their last follow-up. The KM method will also be used to calculate a 95% confidence interval for this cumulative percent at month 6.

[figure not shown]
[figure not shown]
The rate of pregnancies per 100 person-years of follow-up will be summarized by a 95% confidence interval.

For the rate of pregnancies per 100 person-years of follow-up defined as major events, incidence rate will be calculated as follows:

$100 \times (\text{total number of patients with effectiveness endpoint}) / (\text{total person-years of patients included in the effectiveness analysis set})$ where total person-years is equal to (last evaluation date of outcome - first date of administration +1)/365.25 for all patients in the effective analysis set

The difference between the visual analogue scale (VAS) endometriosis pain scores measured at each visit and the measurement taken before the administration of Sayana[®] will be analyzed using paired t-test.

PFIZER CONFIDENTIAL

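### The only required contact is not instructed to ask about pregnancy, and women without a recorded check are excluded or censored with no sensitivity analysis, so the pregnancy estimates may be biased in a direction the documents do not settle

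*Protocol*

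**What the plan says.** Protocol 7.1 states that subjects "will be observed prospectively for a period of 6 months from the enrollment date". After baseline, Protocol 7.2 says "the visits are at the discretion of the investigator and may follow the local usual standard of care"; assessments every 3 months are recommended, not required. The contact written as required is a Follow-up Call, to be made "at least 28 calendar days after the last administration of the study drug within the observational period". Its stated purpose is "in order to collect information on the occurrence of adverse events and concomitant medications". Pregnancy is not named.

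Pregnancy status for contraception users is recorded under *Outcome of administration* (Protocol 7.3.1.5) as pregnant or not pregnant, with an evaluation date and a method. No timing is fixed for that date.

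On the analysis side:

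- SAP 5.2 removes from the efficacy set, among contraception users, "subjects whose check either pregnant or not pregnant at evaluation date on the CRF are not completed". It also removes everyone excluded from the safety set, which under SAP 5.1 includes women whose adverse event status is unknown.
- SAP 8.2.2, like Protocol 7.7.2.2, says "Patients who did not become pregnant will be censored at the time of their last follow-up". Person-years in SAP 8.2.2 stop at the last outcome evaluation.
- SAP 7 allows no imputation and drops missing data.
- Protocol 7.7.1.1 names a single population for all analyses: patients with at least one dose.

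On the reporting side, the table in Protocol 9.1 requires exposure during pregnancy and lack of efficacy to be recorded on the CRF and reported within 24 hours of awareness. For a pregnancy during treatment, Protocol 9.2.3 says "this information must be submitted to Pfizer, irrespective of whether an adverse event has occurred".

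**The concern.** Whether a woman's pregnancy status is known depends on whether she comes back, and coming back may depend on whether she is pregnant. A woman who conceives has less reason to attend for the next contraceptive injection. Equally, a woman may stop because she no longer needs contraception, or may contact the clinic because she is pregnant. Kaplan-Meier censoring and exclusion for a blank check both treat the loss as unrelated to the outcome, and the plan contains nothing that tests this.

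At stake are the two contraceptive effectiveness results: the cumulative percentage pregnant by month 6 and the rate per 100 person-years. Both would describe mainly women with a recorded evaluation. Their confidence intervals would reflect the smaller denominator but not the selection.

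**Working it through.** **1. No planned figure to reproduce.** Protocol 7.5 takes its study size from regulation ("More than 600 subjects should be observed per" the Korean re-examination standard). No event rate, precision or loss to follow-up lies behind the 600. What follows is sensitivity arithmetic, not a correction of a stated number.

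**2. Timing of the call.** SAP 5.1 gives an injection interval of 12 to 14 weeks, that is 84 to 98 days. A call at day 28 falls 28/98 = 29% to 28/84 = 33% of the way through that interval. For a woman with one injection, enrolled on the day of that injection, it leaves about 182.6 − 28 = 155 days of the 6 months without any required contact. The call therefore need not establish month-6 status even if pregnancy were asked.

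**3. Non-returners contribute nothing.** Let f be the fraction of contraception users who do not return and k their 6-month pregnancy risk relative to returners. Neither is in the documents; both are assumed.

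True risk / reported risk = (1 − f) + f·k

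| f | k = 0 | k = 1 | k = 2 | k = 3 | k = 5 |
|---|---|---|---|---|---|
| 10% | 0.90 | 1.00 | 1.10 | 1.20 | 1.40 |
| 20% | 0.80 | 1.00 | 1.20 | 1.40 | 1.80 |
| 30% | 0.70 | 1.00 | 1.30 | 1.60 | 2.20 |
| 40% | 0.60 | 1.00 | 1.40 | 1.80 | 2.60 |

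At f = 20%, k = 3: 0.8 + 0.2 × 3 = 1.40, and 1 − 1/1.40 = 29%, so the reported risk is 29% too low. At k = 1 there is no bias. Below k = 1 the reported risk is too high. The formula fits women who are wholly excluded. For a woman censored part-way, only her unobserved time is affected, so the effect is smaller for the same f and k.

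**4. Some non-returners' pregnancies are captured.** Let c be the share of non-returners' pregnancies that reach the CRF and are counted, while non-returners not known to be pregnant are still dropped. With returner risk p:

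Reported risk = [p(1 − f) + c·f·k·p] / [(1 − f) + c·f·k·p]

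Take p = 1% (assumed), f = 20%, k = 2, so the true risk is 1% × 1.20 = 1.20%. At c = 0.5 the reported risk is (0.008 + 0.002)/(0.800 + 0.002) = 1.247%, a ratio to the truth of 1.04.

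| Reported/true, f = 20% | c = 0 | c = 0.25 | c = 0.5 | c = 0.75 | c = 1 |
|---|---|---|---|---|---|
| k = 1 | 1.00 | 1.06 | 1.12 | 1.19 | 1.25 |
| k = 2 | 0.83 | 0.94 | 1.04 | 1.14 | 1.24 |
| k = 5 | 0.56 | 0.73 | 0.90 | 1.07 | 1.23 |

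The sign changes near c = 0.41 for k = 2 and c = 0.65 for k = 5.

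**5. What the interval does show.** With zero pregnancies, the exact 95% Poisson upper limit is −ln(0.025) = 3.689 events divided by person-years. Taking all 600 as contraception users at half a year each (assumed, best case):

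- nobody lost: 3.689/300 = 1.23 per 100 person-years
- 20% lost: 3.689/240 = 1.54
- 40% lost: 3.689/180 = 2.05

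The interval widens with lost follow-up but carries no allowance for steps 3 and 4.

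**The case against.** The strongest reply is that pregnancy is already covered. Lack of efficacy is a listed example of an adverse event (Protocol 9.2.1), the call collects adverse events, and Protocol 9.1 sends exposure during pregnancy to the CRF whether or not there is an event. The pregnancy check sits within the drug administration record, so the recommended 3-monthly treatment assessments may reasonably include it, and nothing bars the call date from serving as an evaluation date. Protocol 8.2 asks for every effort to document outcome at withdrawal.

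Much of this stands. A reader might infer that a pregnancy mentioned on the call would be lost; the documents say the opposite. What remains is narrower. The reporting duty starts at awareness and nothing tells staff to ask. A negative answer has no stated place in the effectiveness data. Protocol 8.2 names neither pregnancy nor a month-6 contact, and a woman who simply does not return has not withdrawn.

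A reader might also infer that the estimates are too low. The documents do not support that: f, k and c are all unstated, and step 4 shows that the sign can reverse.

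Nor is the loss invisible. SAP 8.2.1 tabulates enrolled, retrieved and analysed cases, and the Basic Results tables include a flow chart of those who started and completed. These show overall loss. They do not isolate contraception users without pregnancy information or bound the effect.

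Finally, this is descriptive, non-interventional surveillance with deliberately open visits and an enrolment number set by the regulator (Protocol 7.9). That argues against adding visits, not against one question on a call already required.

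**Conclusion.** The concern holds as a gap in outcome ascertainment combined with untested exclusion and censoring. The month-6 percentage and the rate per 100 person-years are potentially biased: downward if non-returners have higher risk and their pregnancies go unrecorded, possibly upward if their pregnancies are captured while unconfirmed negatives are dropped.

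Size cannot be fixed from the documents. Over the assumed grid in step 3, with non-returners contributing nothing, true risk runs from 0.60 to 2.60 times the reported risk. No figure in the plan is wrong and no new sample size follows. Because the change is cheap and improves the data whichever way the bias runs, it should be made.

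**What to change.** 1. **Protocol 7.2.** Add pregnancy status since the first injection to the existing call for every contraception user: yes or no, with last menstrual period or test date if yes. Place the call as close to the end of the 6-month observation period as possible. Record yes and no answers alike under *Outcome of administration*, with the call date as evaluation date.
2. **SAP 5.2 and 8.2.2.** Count as an event any pregnancy in the observation period known from any study source: visit, call or exposure-during-pregnancy report. Apply inclusion symmetrically. Keeping women with a blank check only when they are known to be pregnant would make inclusion depend on the outcome. So add a sensitivity analysis on all contraception users with at least one dose (the population in Protocol 7.7.1.1), with those lacking a check contributing time to their last known non-pregnant status. Length of follow-up can still depend on the outcome, which is why item 3 is needed.
3. **Reporting.** Give the number and timing of contraception users excluded, or censored before month 6, with a bound on the month-6 percentage, for example over a stated range of k.

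The cost is one question on a call already required, a little more analysis, and possibly less favourable pregnancy figures. No visit or test is added. If the call can no longer be changed, items 2 and 3 can still be done with the data collected.

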### **7.2.1. Inclusion criteria**

Patients must meet all of the following inclusion criteria to be eligible for inclusion in the study:

1. Subjects or legally authorized representatives of pediatric subjects agree to provide written informed consent form (ie, data privacy statement).

Women subjects who are initiating treatment with Sayana® for the first time as per the local product document for usage Evidence of a personally signed and dated informed consent document indicating that the patient (or a legally acceptable representative) has been informed of all pertinent aspects of the study is required.

### **7.2.2. Exclusion criteria**

Patients meeting any of the following criteria will not be included in the study:

1. Known or suspected pregnancy.
2. Undiagnosed vaginal bleeding.
3. Known or suspected malignancy of breast.
4. Active thrombophlebitis, or current or past history of thromboembolic disorders, or cerebral vascular disease.
5. Significant liver disease.
6. Known hypersensitivity to medroxyprogesterone acetate or any of its other ingredients.
7. Women who are before menarche or who are post-menopausal.
8. Treatment with any investigational agent or device within 30 days prior to the enrollment visit.

### **7.3. Variables**

Variable	Role	Data source(s)	Operational definition
Demographic Characteristics	Baseline characteristics	Medical records	*
Basic Laboratory data	Baseline characteristics	Laboratory test results	*
Concomitant medication	Baseline characteristics	Medical records	*

Variable	Role	Data source(s)	Operational definition
Effectiveness result by investigator	Outcome	Medical records	*
Adverse Event (AE)	Outcome	Medical records	*

\* Refer to Section 7.3.1 data collection

Detail instruction of variable will be included in the CRF.

### 7.3.1. Data Collection

The investigator will observe each enrolled subject for 6 months, prospectively, from the enrollment date. There is no specified visit schedule, because this study is not an interventional study. Safety information will be collected at every visit performed for the subject during the observation period.

#### 7.3.1.1. General Information

- Name of Institution: Record the name of the institution.
- Name of Investigator: Record the name of the physician contracted to conduct the study.
- Department: Record the medical department conducting the study.
- Subject ID: Record 4 digit number per subject registration sequence.
- Confirmation of Data Privacy Statement: If all agreement for using subject's personal and medical information, signature and date are obtained by subject or legally authorized representative, then check the box of 'yes'. If not, check 'no' which means that case is excluded from this study.
- Date of contract: Record the date of contract between the Investigator/Institution and the Sponsor.

#### 7.3.1.2. Demographic Information

- Age: Record the age of the subject.
- Sex: Check 'female'.
- Pregnancy: Check the box next to 'yes' or 'no' and record the method of pregnancy test.
- Weight: Record by kg unit.
- Height: Record by cm unit.
- Purpose of administration: Check either the prevention of pregnancy in women of child bearing potential or management of endometriosis-associated pain.
- VAS at Baseline: If the purpose of administration was management of endometriosis-associated pain, visual analogue scale scores recorded by the subject.

### 7.3.1.3. Medical History

Select either 'yes' or 'no' for past/present disease. If 'yes' then write adequate full name of the disease down as Medical Terminology Dictionary indicates (written by Korean Medical Association) and select either 'past' or 'present' at each disease clause.

### 7.3.1.4. Concomitant Medication/Therapy

The investigator records the medication/therapy which has been administered/conducted continuously at the point of being enrolled in this study or administered/conducted newly after being enrolled. Check either 'yes' or 'no'. If 'yes', record in detail.

- Name of drug/Therapy name: Record generic name in case of single product and record trade name in case of combination product. Also, record name of concomitant therapy.
- Daily total dosage/Frequency: Record the daily total dosage as unit. If not combination drug, avoid recording in tablets, capsules or vials. Record the frequency of concomitant therapy.
- Duration of administration/Duration of therapy: Record the starting/ending date of the medicated drug and concomitant therapy (year/month/day). If the medication and therapy are being continued at the completion of the study, record the starting date date and check in the box next to 'Ongoing'.
- Purpose of administration/Purpose for therapy: Record the purpose of administration or therapy.

### 7.3.1.5. Administrative Status for Sayana®

Sayana® is provided by the investigator's prescription, and Pfizer Korea will not provide Sayana® for this study.

Record the following with regard to administrative status of Sayana®.

- Date of administration: Record the date of each Sayana® therapy (year/ month/day).
- Dose: Record the dose (ml).
- Outcome of administration:  
Record the evaluation date. If the purpose of administration was the prevention of pregnancy in women of child bearing potential, check either pregnant or not pregnant with the method of pregnancy check. If the subject is pregnant, record the first day of last menstrual period to collect the time to pregnancy. (At the time of first Sayana® administration, investigator must ensure the subject is non-pregnant. Also if a sexually active subject is having regular menstrual cycle and was previously not being administered with other contraceptive agent (therefore is having normal menstrual cycle), investigator must ensure that the first Sayana® injection is within 5 days of the subject's normal menstrual cycle. If the subject was previously being administered with other contraceptive agent(s) and is not having normal menstrual cycle, investigator must ensure that the subject is not pregnant by a method decided by the investigator).

If the purpose of administration was management of endometriosis-associated pain, visual analogue scale scores recorded by the subject.

### **7.3.1.6. Safety**

#### **7.3.1.6.1. Adverse Event**

Refer to Section 9 of this protocol and Case Report Form blank form.

#### **7.3.1.6.2. Laboratory Test**

Laboratory test is not mandatory because this study is a non-interventional study. If investigator performed a laboratory test (eg, Serum HCG, CBC, Chemistry and Urine) under their usual practice, the results can be collected. Check ‘not done’ if it is not performed. If ‘done’, record the following in detail.

- Name of laboratory test: Record the item of laboratory test.
- Normal range (unit): Record the normal range and its unit for each recorded item in each institution.
- Date for laboratory test: Record the date with year / month / day.
- Test result before / after medication: Record the test result.

Refer to [Section **Error! Reference source not found..**] of the criteria for determining whether an abnormal objective test finding should be reported as an adverse event. If it meets the criteria, it has to be recorded in the adverse event section of the case report form.

